## **5.8 Qualitative Methods**

All individual interviews and focus groups will be conducted by trained study staff. Interviewers will probe for indicators of the selected qualitative domains as well as for themes that emerge during the individual interviews/ focus groups. The interviews/ focus groups will be digitally audio-taped and transcribed verbatim for qualitative data analyses by a professional transcription service. Interviews/ focus groups will be conducted at a location identified by study staff to assure adequate privacy and confidentiality. Participants will be provided with a separate reimbursement for participation in the individual interview. All identifying information will be removed from the transcripts, and only the research team and the transcribers will have access to the audio interview data. Audio recordings of interviews will be destroyed after the analyses are complete. Consensual Qualitative Research methods will be used to analyze the qualitative data.

### **5.8.1 Individual Semi-Structured Interviews with Participants**

The research team will conduct individual semi-structured interviews with approximately six participants that initiated PrEP at each site. The objective of the individual interviews is to ascertain information about factors that serve as facilitators and barriers in the initiation, acceptability and adherence of PrEP. Three interviews at each site will be conducted between Enrollment and Month 3 visit, and three between Month 3 and Month 6.

Each interview will last approximately 30 to 60 minutes in length among participants who are recruited for and consent to this component of the study. A qualitative interview guide will be developed to address two primary domains (1) factors that facilitate the initiation, acceptability and adherence of PrEP and (2) factors that serve as barriers in the initiation, acceptability and adherence of PrEP.

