### 2.4 Study Design (Qualitative Component)

The primary objective of the qualitative component is to provide a contextual understanding of the multi-

level barriers and facilitators in the initiation, acceptability, and adherence to PrEP for PWID. The qualitative data will provide relevant findings regarding the participants' overall impressions and experiences related to their study participation, including motivations for participating in the study, perceptions about PrEP, reasons that PWID choose to initiate or decline PrEP, and describing the most helpful and least helpful components of study/service uptake for PrEP provided in this study (e.g., experimental services provided such as SMS facilitation). The qualitative component will also describe the individual, cultural, institutional, and geographic-specific barriers and facilitators that influence PWID initiation, utilization and adherence to PrEP, including those critical factors that influence study participation and up-take of PrEP (e.g., substance use, socio-economic indicators, culturally specific psychosocial stressors related to stigma). Importantly, the study will also assess the providers' perspectives on PrEP utilization among PWID, and system-level barriers.

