#### **2. Informed consent**

Prior to screening, every potential participant demonstrating interest in study participation will have to sign the Informed Consent Form (See Appendix III). Consent procedure will be performed by a study staff member responsible for recruitment. In more details, the consent procedure is described in Section 8.

3. Randomization

Consenting participants will be randomized using the functionality in REDCap participant database using a pre-defined allocation schedule stratified by site.

4. Locator information

After signing the ICF, the participant will provide his contact information. Staff members will assure participants that the detailed follow-up information will be deleted if they are not enrolled in the study.

5. Behavioral and psychosocial survey

Structured interviews will be administered by an experienced interviewer using the questionnaire designed by study team (Appendix II). Baseline and follow-up questionnaires will not differ in content. Interview data will be directly entered into the online version of the participant questionnaire at the REDCap platform.

*Intervention provision (intervention staff)*

6. Assess participant's readiness for PrEP adherence

PNs will use a PrEP readiness tool to assess key predictors of PrEP adherence.

7. PrEP discussion

PrEP Education will be provided at each study visit to participants by PrEP Navigators with the option to start/continue, stop, or abstain from usage. A manual will be created for all sites to follow when discussing PrEP with participants based on safety and efficacy language found in the ICF under "Study Purpose".

8. Autonomy supportive adherence counseling

Adherence counseling will be provided to all participants who initiate PrEP at each study visit starting at the enrollment visit. The counseling makes use of self-determination theory that is designed to facilitate the client's integration of PrEP usage into his health behavioral routines and support the client in making his own decisions regarding adherence. Counseling will include the development of client-centered strategies to support the consistent daily adherence of PrEP. This counseling is delivered one-on-one by PrEP navigators during the study visits. The counseling will also include reminders not to share the medication and to contact project staff with questions about product use.

After each counseling session, the PN will fill out the Care Coordination Measurement Tool (CCMT).

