#### Reasons PWID choose to initiate and discontinue PrEP

The baseline and follow-up surveys will assess the main reasons for agreeing to start PrEP and stopping it (if stopped during the study period). The quantitative data will be supplemented by acquiring information about core reasons for initiating or refusing PrEP, based on the individual interview qualitative data from participants.

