### 7.3.2 Secondary Analyses

Analyses for secondary objectives will be mostly descriptive. Line listings as well as summary descriptive statistics including means, medians, and proportions with 95% exact or asymptotic confidence intervals as appropriate at each visit, will be used for the following secondary objectives. Specifically,

- Use GEE or random effects models to describe longitudinal patterns and their correlates of PrEP adherence among participants (e.g.: substance use, sociodemographics, sociocultural factors, risk practices and incarceration)
- To describe side effects and adverse events of PrEP among participants in the PrEP demonstration project. AEs will be tabulated, overall and by grade. For any reasonably common AEs (> 20 events), exploratory analyses will be conducted to assess correlates of the AE, including demographics and duration and patterns of PrEP use, within the limits imposed by the small expected number of events.
- Describe and produce summary plots for longitudinal changes in sexual risk-taking behavior among study participants
- List and summarize reasons PWID choose to initiate or decline PrEP
- List and summarize HIV seroconversions and characteristics of the infection(s) (e.g., viral set point, drug resistance patterns) in participants who initiated PrEP

- Use Kappa-statistics to assess agreement of adherence under different measures.

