### Forms filled by the interviewer:

- PrEP Adherence (visual analog scale [VAS] and 3-item screener, additional block for those who discontinue)
- Client Perception of Coordination Questionnaire (24-items)
- Health Care Climate Questionnaire (15-items/ 5-item short form)
- Care Transition Measure (15-items/ 3-item short form)
- Health Care Climate Questionnaire
- Perceived HIV risk and severity
- Depression scale
- Perceived Competence for PrEP Use
- PrEP Self-Regulation Questionnaire
- PrEP/PEP Awareness
- Satisfaction with PrEP provision, medicines
- Side effects (at baseline – anticipation of SEs, at follow-up impact of SE on adherence)
- Sexual and injection risk behavior (n days injected, n days shared equipment, n days of sex, n days sex without condoms, n partners [of them PLWH])
- Social support (do you plan to tell anyone, have you told anyone, did he help, if did not – why?)
- Stigma (related to PrEP, ARV, PWID)
- Substance use inventory (short)
- Use of reminders (what type of reminders you use)

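### Reasons for refusing PrEP are to come from participant interviews that sample only people who started it, so participants who never start have no planned first-hand source

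*Protocol*

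**What the plan says.** Three places in the protocol promise information on why people do not take up PrEP.

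- Section 2.4 lists among the expected qualitative findings "reasons that PWID choose to initiate or decline PrEP".
- Section 7.1 has a secondary endpoint headed "Reasons PWID choose to initiate and discontinue PrEP". Its text says that the survey data will be supplemented with "core reasons for initiating or refusing PrEP, based on the individual interview qualitative data from participants".
- Section 7.3.2 plans to "List and summarize reasons PWID choose to initiate or decline PrEP".

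Two places determine who supplies the data.

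- Section 5.8.1 limits the participant interviews to "approximately six participants that initiated PrEP at each site", three per site before Month 3 and three after.
- Section 7.1 describes the survey's part as follows: "The baseline and follow-up surveys will assess the main reasons for agreeing to start PrEP and stopping it". Appendix II lists, under the adherence form, an "additional block for those who discontinue". It lists nothing comparable for people who decline.

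Not starting is a permitted choice. The PrEP discussion item in Section 5.2 describes PrEP education at every visit "with the option to start/continue, stop, or abstain from usage".

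**The concern.** The one source that Section 7.1 names for refusal reasons is defined, in Section 5.8.1, so that it leaves out people who never start. If sites follow the protocol as written, barriers to initiation will be described by participants who got past them. Those who did not are likely to have different reasons, and interviews with initiators cannot show how different.

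The trial sets out to assess initiation, acceptability and feasibility (Section 7.1), and client-level barriers to initiation are a secondary objective (Section 2.2), so why some participants do not start is relevant to its purpose. The gap lies in data collection. No later analysis, in a statistical analysis plan or elsewhere, can recover reasons that nobody was asked for.

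**Working it through.** No stated figure is in dispute. The check sets each promise against its source, followed by simple arithmetic for scale.

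**1. Which source serves which reason (Section 7.1, Section 5.8.1, Appendix II)**

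| Reason | Survey, as described | Participant interviews |
|---|---|---|
| Starting | Covered | Covered (initiators) |
| Stopping | Covered, with an extra block | Possible (initiators who later stop) |
| Refusing or never starting | Not mentioned | Named as the source, but never-starters are not sampled |

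Only the third row fails. Both parts of the endpoint as headed, initiation and discontinuation, have a survey source.

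**2. Number of interviews (Section 5.8.1; two sites)**

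6 per site × 2 sites = about 12 participant interviews. Under the sampling rule, 0 of the 12 are with participants who never started.

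**3. Are decliners foreseen?**

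Yes. Section 5.2 allows participants to abstain. Section 4.2 gives dosing directions for those who agree to initiate and lets a participant start after enrollment. Section 7.2 uses a 50% acceptance rate in its worked example.

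**4. How many might there be?**

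The protocol fixes no number. For scale only, decliners = 200 × (1 − acceptance rate).

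- At the worked example's 50%: 200 × 0.50 = 100.
- If the 33% and 67% rows of the Section 7.2 table are also read as acceptance rates: 200 × 0.67 = 134 and 200 × 0.33 = 66. This reading is an assumption, because the table labels that column persistence.

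These are illustrations, not forecasts. Section 7.2 also speaks of each participant being enrolled to receive daily PrEP, and Section 5.2 has navigators make sure that each participant has received a first month's supply. Read literally, those sentences leave few or no decliners.

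**5. Other possible sources**

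- Physician interviews (Section 5.8.2) cover barriers to initiation, but second-hand.
- The navigator focus group (Section 5.8.3) is about resources, the SMS reminders and provision of care.
- An interviewed participant who started late could recall an earlier refusal, but no place is reserved for such a person.
- Survey scales on perceived HIV risk, PrEP awareness, anticipated side effects and stigma could be compared between starters and non-starters. As listed, they do not ask why someone declined.

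Section 7.1 names none of these as the source for refusal reasons.

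**The case against.** The strongest reply is that the gap is narrower than it looks. The endpoint heading concerns initiating and discontinuing, and refusing appears only in the supplementary sentence beneath it. Physicians and late starters will say something about barriers to initiation. The questionnaire itself is not reproduced, and Section 7.1 does not say that the survey covers starting and stopping and nothing else, so an item on not starting may exist. The protocol may also expect nearly everyone to begin PrEP. Finally, this is descriptive work on about a dozen interviews.

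Most of this stands, and it rules out three stronger readings that a reader might infer.

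- That a whole secondary endpoint cannot be answered: it can be, for initiation and discontinuation. Only the refusal part is affected.
- That there is no information at all on refusal: indirect sources exist. What is missing is a planned first-hand source from people who never start.
- That the sample-size section expects acceptance as low as 50%, leaving up to half the participants unrepresented: 50% is a single worked example, neither a floor nor a forecast, and the matching table column is labelled persistence, with 50% as its moderate row.

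The conflict between Sections 5.8.1 and 7.1 survives. The interview guide is still to be written, but a guide cannot reach people whom the sampling rule leaves out. If an unlisted survey item does exist, the protocol should say so, because its description of the survey and its form list both point the other way.

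**Conclusion.** The inconsistency is real and should be corrected. As written, the protocol promises reasons for refusing or declining PrEP in three places, assigns them to the participant interviews, and then limits those interviews to initiators: 0 of about 12 planned interviews are with a participant who never started.

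The conclusion assumes that the survey matches its description in Section 7.1 and Appendix II, and that some enrolled participants will not start, which the protocol permits but does not quantify. The consequence is limited to a descriptive secondary item and one aim of the qualitative component. The randomised comparison of adherence, the randomisation and the safety monitoring are untouched.

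**What to change.** If some participants are expected not to start:

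- Reword Section 5.8.1 so that, within the same total of about six per site and the existing split of three before and three after Month 3, some places are reserved for participants who declined or have not started PrEP. About two per site, one in each period, is a workable example rather than a derived number. Unused places revert to other participants. This gives up to 2 × 2 = 4 interviews with non-starters and leaves at least 12 − 4 = 8 with initiators.
- Adapt the interview guide for people who have not started.
- Add one item on the main reason for not starting PrEP to the baseline and follow-up surveys. At enrollment it should be asked after the PrEP discussion; Section 5.2 lists the survey before it but allows the order to vary.

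The cost is a wording change, one survey item, a small addition to the guide, and about two fewer initiator interviews per site.

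If all participants are in fact expected to start, the simpler course is to remove the references to refusing and declining from Sections 2.4, 7.1 and 7.3.2. That costs nothing in data collection but gives up the question.

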### **5.8.2 Individual Semi-Structured Interviews with Clinical Providers**

The research team will conduct individual semi-structured interviews with all physicians involved in PrEP provision in the study. The objective of the individual interviews is to ascertain information about factors that serve as facilitators and barriers in the initiation, acceptability and adherence of PrEP among PWID. The interviews will be conducted after completion of all Month 3 visits. Each interview will last approximately 30 to 60 minutes in length. A qualitative interview guide will be developed to address the following domains: (1) factors that facilitate the initiation, acceptability and adherence of PrEP and (2) factors that serve as barriers in the initiation, acceptability and adherence of PrEP, (3) resources that were available at the clinic, and (4) discussion of what could have improved their ability to provide care.

### **5.8.3 Focus Groups with PrEP Navigators**

The research team will conduct one focus group with all PNs at the end of the study to elicit feedback on

what resources they believe were necessary to optimally implement a PrEP program. Each focus group will last approximately 60 to 90 minutes in length. A focus group guide will be developed to address the following domains: (1) resources that were available at the clinic (2) resources that were available in the community, (3) resources that were not available during the course of the study, (4) feedback on the uptake and potential of the SMS reminder intervention, and (5) discussion of what could have improved their ability to provide care. The PN team will be consented for the focus group immediately prior to the conduct of the focus group and after all participants have completed the study.

## **5.9 Participants who have Suspected or Confirmed HIV at Screening or During the Study**

In the case of suspected HIV infection at the Screening visit, HIV status will be confirmed using local HIV testing guidelines. Participants who have a reactive or positive HIV test at Screening are not eligible for enrollment, even if subsequent testing indicates that they are not HIV infected.

Participants who have a reactive HIV test result at a follow-up visit will be instructed to discontinue their study medication immediately. According to Ukrainian legislature, HIV diagnosis cannot be made in any setting other than an accredited governmental HIV lab. Therefore, a positive result of rapid testing (regardless of the number of confirmatory runs) will be explained to a subject as preliminary and insufficient to definitively confirm HIV infection, which can be done at specialized health care institutions. As specified in the National HTC guidelines, post-test counseling will provide all details on where the confirmatory testing can be done, and appropriate referrals will be provided.

Any participant who is found to have confirmed HIV infection after Enrollment will be followed at all scheduled visits as described in Appendix I. HIV-infected participants will be followed to contribute information regarding HIV outcomes after PrEP exposure (including viral set point), and to comply with expectations of communities.

HIV-infected participants will also be able to continue receiving assistance in securing HIV medical care. Participants who acquire HIV infection during the study will be asked to provide releases of information that will allow study counselors to consult with providers of HIV medical care to coordinate case management, and to implement other strategies intended to help participants to be retained in medical care and to adhere to treatment regimens. These activities will be logged in PN counselor charts.

## **6.0 SAFETY MONITORING AND ADVERSE EVENT REPORTING**

### **6.1 Safety Monitoring**

Close cooperation between the Investigators, clinical and research teams will be necessary in order to monitor participant safety and to respond to occurrences of toxicity in a timely manner. The team will have regularly scheduled conference calls during the period of study implementation, and additional ad hoc calls will be convened if required.

The study site Coordinators are responsible for continuous close monitoring and management of AEs. Sites are required to follow the detailed SOPs describing methods for AE reporting and toxicity management to ensure that AEs are reported and managed in accordance with the protocol and for alerting the Principal Investigator if unexpected concerns arise.

A sub-group of the Protocol Team, including the Principal Investigator, Clinical Consultant, and Co-Investigators will serve as Study Monitoring Committee (SMC). The SMC provides support to site clinicians regarding individual participant clinical management (toxicity management, clinical holds of study drug, study drug re-challenge, permanent discontinuations, etc.). The Site Coordinators will prepare routine study conduct and safety reports for the SMC, which will meet by conference call approximately monthly and will review safety data during a closed meeting. More frequent or ad hoc reviews of safety reports may be conducted by the SMC as needed. A recommendation to stop the trial may be made by the SMC at any such time that the team agrees an unacceptable type and/or frequency of AEs has been observed. If at any time a decision is made to discontinue the study product in all participants, the PI will notify the Site Coordinators and the responsible IRB expeditiously.

## 6.2 Adverse Event (AE) Reporting

Adverse events (AE) are defined as any untoward medical occurrence experienced by participants during the study, and may or may not have a causal relationship with the treatment. Information regarding all AEs regardless of seriousness or severity will be recorded in the participant's source files. Grade 3 and higher adverse events and all creatinine AEs will be recorded on study CRFs. All SAEs must be reported on AE Log CRF. All AEs that result in a clinical hold or permanent discontinuation of study product are reported on AE Log CRF regardless of grade. Grade 3 and higher clinical AEs will be referred to a study clinician at the time of the visit.

All critical laboratory values will be reported as applicable per site SOPs. Participants who are not present at the study site at the time a laboratory AE requiring retesting or follow-up is identified will be followed as deemed clinically appropriate. With appropriate permission of the participant, and whenever possible, records from non-study medical providers related to untoward medical occurrences will be requested and required data elements will be recorded on study CRFs and/or in the participant's medical chart. All AEs regardless of severity will be followed clinically, until the AE resolves or stabilizes as per the appropriate toxicity algorithm. AEs will be assessed for all participants, regardless if they continue PrEP or not, after enrollment through the final study visit.

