### 5.3 Month 1, 3 and Month 6 (exit visit)

At months 1 and 3, the participants will visit the clinical site to complete the assessments and receive the medication supply for next two (at month 1) three (at month 3) months. At month 6, participants will not receive medication as a part of the study, but will be referred to other available PrEP providers in Kyiv. The following procedures will be included.

- Verify locator information
- Behavioral and psychosocial survey
- Self-reported study product adherence assessment
- PrEP discussion
- PrEP Navigation and study product supply
- Autonomy supportive adherence counseling
- SMS reminder customization

- HIV/ STI behavioral risk-reduction counseling, provision of prevention supplies
- Medical history including but not limited to co-morbidities, concomitant medications, HIV risk history
- Symptom-driven physical exam
- AE Assessment
- HIV rapid test – at months 3 and 6.
- DBS storage for pharmacology testing
- Urine storage for substance use testing

The exit visit will include all procedures for Month 3, except for PrEP provision and related counseling and SMS customization.

#### 5.4 Months 2, 4, 5

Monthly assessments between the PrEP dispensing visits (Enrollment and 3-month) will be conducted by research staff **by telephone**. The following procedures will be included.

- Review and update locator information
- Self-reported study product adherence assessment

Self-reported PrEP adherence for all participants will be assessed using both a visual analogue scale (VAS) and a new 3-item self-report measure. The VAS is empirically validated, consistently under-reports adherence, but effectively measures a “difference” in adherence that changes in response to an intervention. The 3-item adherence self-report scale showed good psychometric characteristics and good construct validity when compared with an drug monitoring standard. Two self-report adherence measures are often recommended.

- PrEP discussion
- Autonomy supportive adherence counseling
- SMS reminder customization

Experimental arm participants will have an opportunity to change the parameters of the SMS reminders.

- HIV/ STI behavioral risk-reduction counseling

After the standard risk-reduction counseling, the participants will be invited to visit the harm reduction site to receive supplies.

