**APPENDIX I - SCHEDULE OF EVALUATIONS AND PROCEDURES**

	Pre-screening	Enrollment	Month 1, 3	Month 2,4,5 (by phone)	Month 6 (exit)	Interim visits
Administrative and Behavioral Evaluations/ Procedures						
Pre-screening	x					
Eligibility screening and demographic information		x				
Informed Consent, randomization		x				
Locator information		x	x	x		x
Behavioral and psychosocial survey		x	x		x	
Initial PrEP adherence readiness assessment (PN)		x				
Self-reported study product adherence assessment (PN)			x	x	x	x
Individual Interview for selected participants						x
Staff Focus Group (after all participants complete)						x
Intervention provision						
PrEP Discussion		x	x	x	x	x
Autonomy Supportive Adherence Counseling		x	x	x		x
PrEP Navigation and study product supply		x	x			x
SMS reminder customization 		x	x	x		x
SMS reminder 		x	xx	xx		
HIV/ STI behavioral risk-reduction counseling		x	x		x	x
Provision of prevention supplies		x	x		x	x
Clinical Evaluations/ Procedures						
Medical history including medications		x				
Symptom-Driven Physical Examination		x				
Laboratory Evaluations/Procedures						
HIV screening testing		x	x 		x	
HBsAg testing		x			x	
Renal function tests (creatinine)		x				
Calculated creatinine clearance		x				
DBS storage for possible Pharmacology testing		x	x		x	

 Experimental arm only.

 Month 3 only

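### Section 7.3.2 tabulates adverse events of every grade, but section 6.2 sends most Grade 1-2 events to source files only, so a table built from the CRFs would undercount mild events and shift the grade mix upward

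*Protocol*

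**What the plan says.** **Recording.** Section 6.2 requires every AE, whatever its severity, to be noted in the participant's source file. CRF entry is narrower: "Grade 3 and higher adverse events and all creatinine AEs will be recorded on study CRFs". Two further routes exist. All serious AEs go on the AE Log, and "All AEs that result in a clinical hold or permanent discontinuation of study product are reported on AE Log CRF regardless of grade". Section 6.3.1 requires all AEs to be graded.

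**Analysis.** Section 7.1 names adverse events as a secondary endpoint, graded from reported clinical and laboratory events, with no lower limit on grade. Section 7.3.2 sets the task: "To describe side effects and adverse events of PrEP among participants in the PrEP demonstration project". It then says "AEs will be tabulated, overall and by grade", and adds: "For any reasonably common AEs (> 20 events), exploratory analyses will be conducted to assess correlates of the AE". Those correlates include demographics and the duration and pattern of PrEP use. The same sentence acknowledges that few events are expected.

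**Schedule.** The Month 1, 3 and 6 procedures in section 5.3 include "AE Assessment", medical history and a symptom-driven examination. Appendix I has no AE row. Its rows for medical history and "Symptom-Driven Physical Examination" are marked at Enrollment only.

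**The concern.** The collection rule and the analysis do not fit together. The rule suits a report of severe, serious, renal and treatment-limiting events. The analysis asks for a description of all side effects, broken down by grade.

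A table drawn from the CRFs under an all-grade heading would hold complete Grade 3+ data and a selected remnant of Grade 1-2 data. A reader would take the overall count as the burden of side effects of daily PrEP in people who inject drugs, and the grade columns as its severity profile. Both would partly be products of the recording rule. AEs are a secondary endpoint and the primary adherence comparison is untouched, but the safety description is what others would use to judge tolerability in this population.

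**Working it through.** The protocol states no AE rate, grade mix or AE-based sample size, so there is no figure of its own to reproduce. The check is a comparison of sections, followed by a short argument on direction.

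**1. Which events have a required route to a CRF (section 6.2)?**

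| Event | Source file | CRF |
|---|---|---|
| Grade 3 or higher | yes | yes |
| Creatinine AE, any grade | yes | yes |
| Serious AE, any grade | yes | yes |
| AE causing a hold or permanent stop, any grade | yes | yes |
| Any other Grade 1-2 AE | yes | no requirement |

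**2. Do the exceptions fill the gap?** Not on the text. Section 6.6.1 leaves continuation of the drug at Grades 1-2 to the site investigator, so a mild event need not lead to a hold. Appendix I marks creatinine at Enrollment only, and section 5.3 lists no creatinine test at follow-up, so scheduled testing can add few creatinine events. The side-effect item in Appendix II asks about anticipated effects at baseline and their impact on adherence later; it is not a graded AE record.

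**3. Direction.** Let *s* be the true share of AEs that are Grade 1-2, and *c* the fraction of those that reach a CRF. Take Grade 3+ capture as complete.

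- Share of all AEs captured = (1 − s) + s·c = 1 − s(1 − c). This is below 1 whenever s > 0 and c < 1.
- Tabulated Grade 3+ share = (1 − s) / [(1 − s) + s·c]. This exceeds the true share 1 − s whenever 0 < s < 1 and c < 1.

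The overall count is therefore too low and the mix too severe for every c below 1.

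**4. Illustration only.** Neither *s* nor *c* is in the protocol. Assumed ranges: s = 70% to 95%, c = 2% to 20%.

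| s | c | AEs captured | Tabulated Grade 3+ share | True Grade 3+ share |
|---|---|---|---|---|
| 70% | 2% | 0.30 + 0.014 = 31.4% | 0.30/0.314 = 95.5% | 30% |
| 70% | 20% | 0.30 + 0.14 = 44.0% | 0.30/0.44 = 68.2% | 30% |
| 90% | 10% | 0.10 + 0.09 = 19.0% | 0.10/0.19 = 52.6% | 10% |
| 95% | 2% | 0.05 + 0.019 = 6.9% | 0.05/0.069 = 72.5% | 5% |
| 95% | 20% | 0.05 + 0.19 = 24.0% | 0.05/0.24 = 20.8% | 5% |

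Across these assumptions the CRFs hold 6.9% to 44.0% of all AEs. The width of that range shows why no single figure should be quoted.

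**5. The exploratory rule.** The threshold in "For any reasonably common AEs (> 20 events), exploratory analyses will be conducted" means 21 or more. If it is applied to CRF counts, an AE type that occurs only at Grade 1-2 needs 21/c true events to qualify: 21/0.20 = 105 at c = 20%, and 21/0.02 = 1,050 at c = 2%. Common mild effects are thus the ones most likely to be missed.

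**6. Correlates.** Section 6.2 assesses AEs in all participants, whether or not they continue PrEP. A mild, non-serious, non-creatinine AE in someone who is off PrEP cannot cause a hold or a stop, so it has no required route to the CRF. The same event in someone on PrEP has one. The recording rule alone can therefore produce an association between mild AEs and PrEP use, which is one of the relationships that section 7.3.2 wants to explore.

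**The case against.** The strongest reply is that section 7.3.2 names no data source. All AEs are to be graded and held in source files, so the raw material for a full table is planned to exist. Section 6.1 refers AE reporting methods to SOPs that are not shown, and a statistical analysis plan may exist. This stands in part: the undercount depends on the table being built from CRF data, and a reader who concludes that the published table must be wrong goes further than the text allows. But the protocol describes no abstraction of Grade 1-2 events, and an analysis plan can relabel a table without supplying events that were never entered.

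Three other inferences are tempting and are not supported.

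- *Appendix I shows that AEs go unassessed, and so adds to the undercount.* Section 5.3 lists the assessment at Months 1, 3 and 6, section 6.2 requires it through the final visit, and section 5.0 calls the appendix an overview. The missing row is a schedule inconsistency.
- *More than 20 events implies a minimum share of the 200 participants.* The rule counts events, and one person may contribute several. Lower-grade creatinine and hold events count as well. The rule is conditional and exploratory, so being seldom met would not in itself be a flaw.
- *The size of the undercount can be stated.* Any percentage needs AE rates and capture fractions that the protocol does not give.

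It can also be said that restricting CRF entry to the more severe events is a legitimate economy. That is so. The fault is not the economy but pairing it with an all-grade table.

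**Conclusion.** The point holds in a conditional form. Sections 6.2 and 7.3.2 conflict: the protocol requires CRF data on a selected set of AEs and plans a description of all of them. If the table is built from the CRFs, it will undercount Grade 1-2 events and overstate the Grade 3+ share. The correlate analysis with PrEP use inherits the same selection.

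This rests on three assumptions: CRF data feed the table, Grade 3+ capture is complete, and at least some Grade 1-2 events fall outside the exceptions. Given these, the direction is certain; the size is unknown. The primary comparison is unaffected, but what the safety endpoint can support changes, so the conflict should be resolved before the data are tabulated.

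**What to change.** Choose one of two routes.

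1. **Collect what the table needs.** Amend section 6.2 so that AEs of every grade are entered on the AE Log CRF from the source records, where they must already be noted and graded. The cost is some extra data entry. Section 7.3.2 can then stand.
2. **Restrict the table to what is collected.** Amend section 7.3.2 so that the table and the exploratory rule for frequent events cover only Grade 3+, creatinine, serious and hold-or-stop AEs. Label both accordingly, and claim no overall AE rate or Grade 1-2 distribution. This costs a sentence or two, but gives up a graded description of mild side effects.

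Route 1 is preferable if describing tolerability in this population remains an aim.

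Separately, reconcile Appendix I with section 5.3: an AE row at Months 1, 3 and 6, and agreement between the two on medical history and symptom-driven examination at follow-up. This is a table edit.
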